#### **9.1.7. Time Period and Frequency for Collecting AE, SAE, and Other Reportable Safety Event Information**

All AEs, SAEs, and other reportable safety events that occur after the consent form is signed but before first study treatment must be reported by the investigator *if they cause the subject to be excluded from the study or are the result of a protocol-specified intervention*, including but not

limited to washout or discontinuation of usual therapy, diet, or a procedure. SAEs and ECIs will be collected for 90 days after the end of treatment or 30 days after the end of treatment if the subject initiates new post treatment cancer therapy, whichever is earlier.

All AEs from the time of first study treatment through 30 days following cessation of study treatment must be reported by the investigator.

All SAEs or ECIs, from the time of first study treatment through 90 days following cessation of study treatment, or 30 days following cessation of study treatment if the subject initiates new post-treatment cancer therapy, whichever is earlier must be reported by the investigator.

All pregnancies and exposure during breastfeeding, from the time of first study treatment through 90 days following cessation of study treatment, or 30 days following cessation of study treatment if the subject initiates new post-treatment cancer therapy must be reported by the investigator.

Additionally, any SAE brought to the attention of an investigator at any time outside of the time period specified above must be reported immediately to the Sponsor if the event is considered to be study drug related.

#### **9.1.8. Reporting of SAEs or ECIs**

Within 24 hours of identifying an SAE/ECI, regardless of the presumed relationship to the investigational product, the investigator or qualified designee must complete the SAE Report Form and submit it to the Sponsor or its designee. Instructions for SAE/ECI reporting will be provided by the CRO. The sponsor is responsible for reporting certain SAEs as expedited safety reports to applicable regulatory authorities, ethics committees, and participating investigators, in accordance with ICH Guidelines and/or local regulatory requirements. The sponsor may be required to report certain SAEs to regulatory authorities within 7 calendar days of being notified about the event; therefore, it is important that investigators submit additional information requested by the sponsor or delegate as soon as it becomes available.

Investigators should provide all available information at the time of SAE Report Form completion. Investigators should not wait to collect additional information to fully document the event before notifying the Sponsor or its designee of an SAE/ECI. When additional information becomes available, investigators should submit a follow-up SAE Report Form (separate from the initial report form) with the new information. Any follow-up information to an SAE/ECI also needs to be provided the Sponsor or its designee within 24 hours of learning of the new information.

#### **9.2. Laboratory Test Abnormalities**

Laboratory abnormalities that constitute an AE in their own right (considered clinically meaningful, induce clinical signs or symptoms, require concomitant therapy, or require changes in study drug) should be recorded on the AE eCRF. Whenever possible, a diagnosis rather than a symptom should be provided (e.g., "anemia" instead of "low hemoglobin"). Laboratory abnormalities that meet the criteria for AEs should be followed until they have returned to normal or an adequate explanation of the abnormality is found. When an abnormal laboratory test result corresponds to a sign or symptom of a previously reported AE, it is not necessary to separately record the laboratory test result as an additional event.

Laboratory abnormalities that do not meet the definition of an AE should not be reported as AEs. A Grade 3 or 4 (severe) AE does not automatically indicate an SAE unless it meets the definition of serious, as defined in [Section 9.1.2](#).

### 9.3. Pregnancy

If a subject inadvertently becomes pregnant while on study treatment with NC525 the subject will be immediately discontinued study treatment. The site will contact the subject at least monthly and document the subject's status until the pregnancy has been completed or terminated. The outcome of the pregnancy will be reported to the Sponsor without delay and within 24 hours if the outcome is a serious adverse experience (e.g., death, abortion, congenital anomaly, or other disabling or life-threatening complication to the mother or newborn). The study investigator will make every effort to obtain permission to follow the outcome of the pregnancy and report the condition of the fetus or newborn to the Sponsor.

When a pregnancy has been confirmed in a subject (or a male subject's partner) during maternal or paternal exposure to study drug within 90 days of the last dose of study treatment or 30 days if a new post treatment cancer therapy is initiated, the following procedures should be followed to ensure subject safety:

- The study drug must be discontinued immediately (female subjects only).
- Consent must be obtained from female partners of male subjects.
- The investigator must complete and submit the Clinical Trial Pregnancy form to the sponsor or its designee within 24 hours of learning of the pregnancy.
- A serum pregnancy test must be performed to confirm the urine pregnancy test result (female subjects only).

If a negative serum test does not confirm the urine pregnancy test result, then:

- The investigator will use his or her expert judgment, based on an assessment of the potential benefit/risk to the subject, to determine whether it is in the subject's best interest to resume study drug and continue participation in the study.
- The EOT visit evaluations must be performed (female subjects only).

Pregnancy should be recorded on a Clinical Trial Pregnancy form and reported by the investigator to the sponsor or its designee. Pregnancy outcomes of spontaneous abortion missed abortion, benign hydatidiform mole, blighted ovum, fetal death, intrauterine death, miscarriage, and stillbirth must be reported as serious events (Important Medical Events). If the pregnancy continues to term, the outcome (health of infant) must also be reported. Pregnancy follow-up information should be recorded on the same form and should include an assessment of the possible causal relationship to the study treatment to any pregnancy outcome.

**Any SAE occurring during pregnancy must be recorded on the SAE report form and submitted to the sponsor or designee.**

#### **9.4. Warnings and Precautions**

Special warnings or precautions for the study treatment, derived from safety information collected by the sponsor or its designee, are presented in the NC525 IB. Additional safety information collected between IB updates will be communicated to Investigators as it becomes available. Any important new safety information should be discussed with the subject during the study, as necessary, and provided to the IRB. If new significant risks are identified, they will be added to the ICF.

#### **9.5. Procedures for Cohort Safety Review and Dose Escalation Meetings**

Telephone conferences will be scheduled by the sponsor, or sponsor's delegate, with the Clinical Study Team to review cohort-specific data and overall safety data, make dose escalation/de-escalation decisions, evaluate dose increment modifications, agree on dose finding, adjudicate individual high-grade AEs as potentially dose-limiting, and guide other major study decisions.

## 10. STATISTICS

This section outlines the statistical analysis strategy and procedures for the study. If, after the study has begun, but prior to any final database lock, changes are made to primary and/or key secondary hypotheses, or the statistical methods related to those hypotheses, then the protocol will be amended (consistent with ICH Guideline E-9). Changes to exploratory or other non-confirmatory analyses made after the protocol has been finalized, but prior to final database lock, will be documented in a supplemental SAP (SAP) and referenced in the Clinical Study Report (CSR) for the study. Post hoc exploratory analyses will be clearly identified in the CSR.

Tabular summaries will be presented by dose groups. Categorical data will be summarized by the number and percentage of subjects in each category. Continuous variables will be summarized by descriptive statistics including mean, standard deviation, median, minimal, and maximal values. All analyses, unless specified otherwise, will be based on as-treated population, which includes all subjects who receive any dose of NC525. Additional details of statistical analyses will be described in a supplemental SAP.

### 10.1. Statistical Analysis Overview

Key elements of the statistical analysis plan are summarized in [Table 13](#).

**Table 13: Key Elements of the Statistical Analysis Plan (SAP)**

Element	Plan for analysis
Study Design Overview	This is an open-label, non-randomized, Phase 1 study to determine the safety and tolerability of NC525. This study will also assess the clinical benefit in subjects with advanced myeloid neoplasms.
Analysis Populations	Safety Analysis Set (SAS): The SAS will include all the subjects who receive any amount of NC525 and will be used for summaries and analyses of safety data.  PK Analysis Set (PAS): The PAS will include all the subjects whose blood samples are collected for PK analysis and will be used for PK data summaries and analyses.  Full Analysis Set (FAS): The FAS includes all subjects enrolled in the study who received at least one full dose of NC525. The FAS will be used for summaries and analyses of all data that are not safety or PK
Primary Endpoint(s)	

1) Safety and tolerability will be assessed by monitoring the frequency, duration, and severity of adverse events (AEs). Note: Toxicity grading per NCI CTCAE v5.0

2) The recommended Phase 2 dose (RP2D) of NC525 in subjects with advanced myeloid neoplasms.

3) The MAD, PAD, and MTD of NC525 will be defined in subjects with advanced myeloid neoplasms.

Secondary Endpoints	
 
1) Assessment of anti-leukemia activity/efficacy will be used to evaluate the clinical benefit of NC525, including:             
 
a. Objective Response (OR)                   
 
i. CR, CRi, or CRh and MLFS
 
 
 
b. Event-free survival (EFS), and
 
c. Overall survival (OS)
 
 
 
2) Assessment of time to achieve response, defined as CR, CRi, or CRh             
 
a. To evaluate the time to achieve an objective response from Cycle 1 Day 1 to day remission is achieved as defined per protocol
 
 
 
3) Assessment of PK of NC525 concentration(s) in serum, as well as assessment of the PK/PD profile
 

Statistical Methods for Efficacy/ Immunogenicity/ Pharmacokinetic Analyses	
Using the FAS, all the efficacy data will be summarized by dose level and cohort.
 
The PK analyses will be based off the PAS, and PK time-concentration data will be summarized, listed, and plotted. PK parameters (<math>AUC_{0-168}</math>, <math>AUC_{0-\infty}</math>, <math>C_{max}</math>, <math>t_{1/2}</math>, etc.) derived from time-concentration data will be summarized.

Treatment Assignment	This is an open-label study.
Statistical Methods for Safety Analyses	All the safety data in the SAS will be summarized and listed by dose level and cohort.
Interim Analyses	No formal interim analysis is planned. However, the safety, PK and efficacy data will be regularly reviewed and monitored for decisions involving the dose escalation and safety expansion parts of the study.
Multiplicity	Individual cohorts will be evaluated independently.
Sample Size and Power	
The overall study sample size is approximately 63.
 
Dose Escalation: The planned sample size is up to 30 subjects.
 
Safety Expansion: The planned sample size is up to 33 subjects

Abbreviations: AE = adverse event; AUC = area under the curve;  $C_{max}$  = maximum concentration of drug; CR = complete response; CTCAE = Common Terminology Criteria for Adverse Events; FAS = Full Analysis Set; NCI = National Cancer Institute; OR = objective response; PAS = Pharmacokinetics Analysis Set; PD = pharmacodynamics; PK = pharmacokinetics; PR = partial response; RP2D = recommended Phase 2 dose; SAS = Safety Analysis Set;  $t_{1/2}$  = half-life.

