**Table 5: Infusion Reaction Dose Modification and Treatment Guidelines (NC525)**

NCI CTCAE v5.0 Grade of Sign or Symptom of Infusion-Related Reaction	Treatment	Premedication at Subsequent Dosing
Grade 1 Mild reaction	Increase monitoring of vital signs as medically indicated until the subject is deemed medically stable in the opinion of the investigator.	None
Grade 2  Requires therapy or infusion interruption but responds promptly to symptomatic treatment	Stop Infusion.  Additional appropriate medical therapy may include but is not limited to: 

• IV fluids

• Antihistamines

• Acetaminophen

• NSAIDs

• Narcotics

• Prophylactic medications indicated for <math>\leq 24</math> hrs

	Subject may be premedicated 1.5 h our ( $\pm$ 30 minutes) prior to infusion of study intervention with:  Diphenhydramine 50 mg po (or equivalent dose of antihistamine).  Acetaminophen 500-1000 mg po (or equivalent dose of analgesic).

NCI CTCAE v5.0 Grade of Sign or Symptom of Infusion-Related Reaction	Treatment	Premarketation at Subsequent Dosing
	
Increase monitoring of vital signs as medically indicated until the subject is deemed medically stable in the opinion of the investigator.
 
If symptoms resolve within 1 hour of stopping drug infusion, the infusion may be restarted at 50% of the original infusion rate (e.g., from 100 mL/hr. to 50 mL/hr.). Otherwise, dosing will be held until symptoms resolve and the subject should be premedicated for the next scheduled dose.
 
Discontinue study treatment permanently for subjects who develop a Grade 2 or higher hypersensitivity reaction despite adequate premedication.
	

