
Grades 3 or 4
 
Grade 3: Prolonged (i.e., not rapidly responsive to symptomatic medication and/or brief interruption of infusion); recurrence of symptoms following initial improvement; hospitalization indicated for other clinical sequelae (e.g., renal impairment, pulmonary infiltrates)
 
Grade 4: Life-threatening
	
Stop Infusion.
 
Additional appropriate medical therapy may include but is not limited to:
 
 
• IV fluids
 
• Antihistamines
 
• Acetaminophen
 
• Oxygen
 
• Corticosteroids
 
• Epinephrine**
 
• NSAIDs
 
• Narcotics
 
• Pressors
 
• Ventilator
 
 
Increase monitoring of vital signs as medically indicated until the subject is deemed medically stable in the opinion of the investigator.
 
Hospitalization may be indicated.
 
**In cases of anaphylaxis, epinephrine should be used immediately.
 
Subject is permanently discontinued from further study drug treatment.
	
No subsequent dosing

Abbreviations: IV = intravenous; NSAID = nonsteroidal anti-inflammatory drugs; po = orally.

Appropriate resuscitation equipment should be available at the bedside and a physician readily available during the period of drug administration. For further information, please refer to the Common Terminology Criteria for Adverse Events v5.0 (CTCAE) at <http://ctep.cancer.gov>.

The above table is the recommended guidance, however subjects should be managed per institutional guidelines.

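### The efficacy analysis set leaves out treated subjects who never receive a full dose, which is expected to raise the reported response rate

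*Combined protocol and SAP*

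**What the plan says.** Section 10 sets a general default: "All analyses, unless specified otherwise, will be based on as-treated population, which includes all subjects who receive any dose of NC525". Table 13 (Section 10.1) then names specific sets. For safety, "The SAS will include all the subjects who receive any amount of NC525". The FAS sets a higher bar: "The FAS includes all subjects enrolled in the study who received at least one full dose of NC525". Its scope is wide: "The FAS will be used for summaries and analyses of all data that are not safety or PK". The efficacy row of the same table confirms this: "Using the FAS, all the efficacy data will be summarized by dose level and cohort". Objective response (OR), time to response, event-free survival (EFS) and overall survival (OS) therefore all rest on the FAS. The documents do not define what makes a dose full.

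Table 5 (Section 5.8.4) decides what follows an interrupted infusion.

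- After a Grade 2 reaction: "If symptoms resolve within 1 hour of stopping drug infusion, the infusion may be restarted at 50% of the original infusion rate". Failing that, the subject is premedicated for the next planned dose.
- After a Grade 3 or 4 reaction the infusion stops and "Subject is permanently discontinued from further study drug treatment".
- Table 5 also ends treatment for a hypersensitivity reaction of Grade 2 or higher that occurs despite adequate premedication.

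Section 10.2.2 gives the response rule at the recommended Phase 2 dose (RP2D). The expansion may stop if 2 or fewer of the first 14 subjects respond, and the treatment is regarded as promising if 9 or more of 28 respond. No analysis set is named for either count.

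Appendix 6, to which Section 1.2.3.1 refers for outcome measures, defines OS and EFS for all patients in a trial, measured from registration when there is no randomization. Section 1.2.3.1 also has a non-evaluable response category that takes in early deaths and withdrawals before assessment.

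**The concern.** Entry to the FAS depends on something that happens after treatment starts and that the drug itself can cause. A subject whose first infusion is cut short by a severe reaction and who is then taken off the drug is in the safety set but in no efficacy denominator. That subject is very unlikely to be a responder, so removal shrinks the denominator and leaves the numerator alone. The same subject would belong in the non-evaluable category of Section 1.2.3.1 and in the OS and EFS populations of Appendix 6, but is removed before being classified.

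The number of such subjects may be small, but so are the groups: up to 14 per expansion dose and 28 at the RP2D. If severe first-infusion reactions were more frequent at one dose than at another, the efficacy summaries by dose that feed the RP2D choice would be shifted unequally. Because a full dose is undefined and the trial is open label, membership of the set could also be argued once responses are known.

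**Working it through.** **Inputs.** The response rule and its operating characteristics come from Section 10.2.2 and Table 15. The set definitions come from Table 13 and the discontinuation rules from Table 5. The fraction of treated subjects who never get a full dose, d, is not in the documents. It is assumed here at 2%, 5% and 10%, and the excluded subjects are assumed not to respond.

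**1. Reproduce Table 15.** With X1 and X2 independent Binomial(14, p):

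- P(early stop) = P(X1 ≤ 2)
- P(promising) = sum over x1 = 3 to 14 of P(X1 = x1) × P(X2 ≥ 9 − x1)
- Average N = 14 + 14 × (1 − P(early stop))

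| p | Early stop, computed / Table 15 | Promising, computed / Table 15 | Average N, computed / Table 15 |
|---|---|---|---|
| 0.2 | 44.81% / 44.81% | 8.67% / 8.67% | 21.73 / 21.7 |
| 0.4 | 3.98% / 3.98% | 84.06% / 84.06% | 27.44 / 27.4 |
| 0.5 | 0.65% / 0.65% | 97.84% / 97.84% | 27.91 / 27.9 |

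The plan's figures are reproduced, so the calculation can be used below.

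**2. Effect on the reported rate.** With n treated, r responders and k non-responders excluded, the rate on all treated is r/n and on the FAS r/(n − k).

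| | All treated | k = 1 | k = 2 | k = 3 |
|---|---|---|---|---|
| n = 28, r = 9 | 9/28 = 32.1% | 9/27 = 33.3% | 9/26 = 34.6% | 9/25 = 36.0% |
| n = 14, r = 3 | 3/14 = 21.4% | 3/13 = 23.1% | 3/12 = 25.0% | 3/11 = 27.3% |

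One excluded subject moves the rate by 1.2 points at 28 and 1.7 points at 14. For scale, the binomial standard error of 9/28 is √(0.321 × 0.679 / 28) = 0.088, or about 8.8 points.

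**3. Effect on the decisions.** Both rules count responses.

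- *If the 14 and 28 places are filled by treated subjects,* excluding non-responders cannot change whether 3 or 9 responses are reached. The decisions and Table 15 stand.
- *If the places are filled by full-dose subjects,* so that excluded subjects are replaced, the rate among those counted is p/(1 − d):

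| Treated-population rate | d | p/(1 − d) | P(promising) |
|---|---|---|---|
| 0.20 | 0 | 0.200 | 8.67% |
| 0.20 | 2% | 0.204 | 9.61% |
| 0.20 | 5% | 0.211 | 11.21% |
| 0.20 | 10% | 0.222 | 14.51% |
| 0.40 | 0 | 0.400 | 84.06% |
| 0.40 | 2% | 0.408 | 86.05% |
| 0.40 | 5% | 0.421 | 88.82% |
| 0.40 | 10% | 0.444 | 92.76% |

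**4. Which case do the documents favour?** Section 10.2.2 is silent. Section 3.4.2 allows replacement of a subject who leaves treatment before the end of the dose-limiting toxicity (DLT) period for a reason other than a DLT. Table 6 (Section 5.9.1) lists an adverse reaction leading to withdrawal as a DLT. Section 3.2.1 counts a subject who stopped early for an adverse event as evaluable. Together these suggest that a subject withdrawn for a drug reaction keeps the place. They were written for DLT evaluation, however, and do not settle the response count.

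**The case against.** A fair defence has several parts, and much of it stands.

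- **A reader might infer that Table 13 contradicts the any-dose default in Section 10.** It does not. The default applies unless something else is specified, and Table 13 specifies something else. This is a choice of population.
- **A reader might infer that every subject with an incomplete first infusion is dropped.** The definition asks for one full dose at any time. After a Grade 2 reaction, Table 5 lets the infusion restart or dosing go on at the next visit, and either route can bring the subject into the FAS. Only those who never receive a full dose are lost.
- **A reader might infer that the 3-of-14 and 9-of-28 decisions are inflated.** That needs replacement of excluded subjects, which Section 10.2.2 does not state and the sections in step 4 point against.
- **A reader might infer an upward bias in every efficacy endpoint.** The argument fits OR. For OS the direction is unknown, since a subject stopped early may go on to other therapy or transplant. For EFS, Appendix 6 censors a living non-evaluable patient at day 1, so including that patient adds no follow-up; an early death without assessment would count as an event.
- **The practical weight is limited.** Efficacy is a secondary endpoint, Section 3.3 rules out formal comparisons, and the RP2D rests on DLTs, safety, tolerance and biological activity as well as response. A failed first infusion stays visible in the safety tables, although the note under Table 17 leaves infusion reactions out of the toxicity rate used for the expansion stopping rule.
- **A supplemental SAP may add detail.** It may, but Table 13 already fixes the definition and its use.

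What remains is that the efficacy denominator is conditioned on an event the drug can cause, with no stated reason for doing so.

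**Conclusion.** The point holds in a limited form. The FAS excludes treated subjects who never receive a full dose, and Table 5 gives a concrete route to that exclusion. The reported response rate is expected to be too high whenever such a subject occurs and does not respond; if none occurs, there is no effect. In the illustration, 9 of 28 moves from 32.1% to between 33.3% and 36.0% for one to three exclusions, which is small beside the sampling error but in a predictable direction. The FAS also does not match the all-patients populations of Appendix 6 for OS and EFS.

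The rise in the chance of a promising result at 0.20, from 8.7% to between 9.6% and 14.5%, applies only if excluded subjects are replaced, and only for the assumed 2% to 10% excluded. The documents do not show that this will happen. It is a reason to state which subjects the rule counts, not evidence that the rule is biased as planned.

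**What to change.** In Table 13 and Section 10.2.2:

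1. Base OR, EFS and OS on all subjects who receive any amount of NC525, which is the Safety Analysis Set. Section 7.1 treats the day of enrolment as the day of treatment, so this is the closest available match to Appendix 6.
2. For OR, count subjects without a response assessment as non-responders, and still report how many were non-evaluable.
3. State that the 14- and 28-subject response rules count this population. Table 15 then applies as printed.
4. Keep the full-dose set as a sensitivity analysis, with a definition of a full dose that says how interrupted and restarted infusions are classed.

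The cost is wording only: no extra subjects, visits or data. The reported response rate may be slightly lower.
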